2.2.3. Sample Size Considerations

Part 1:

The sample size of this first-in-human clinical study was selected with the goal of balancing between safety and tolerability considerations in dose escalation and obtaining sufficient initial information related to the safety and biological activities of BIIB105. Sample sizes of 6 participants receiving active treatment in lower dose Cohorts A and B will allow an █% or greater probability to observe at least 1 occurrence of an AE with event rates of █% or greater. The sample size of 9, 36, and 12 participants exposed to active doses in Cohorts C1, D1, and D2, respectively, allow an █% or greater probability to observe at least 1 occurrence of an AE with event rates of █%, █%, and █%, or greater, respectively.

Cohort C2 will expose 3 participants with polyQ-ALS to active treatment as part of additional dose escalation step specifically for participants with intermediate-repeat CAG expansions in *ATXN2* gene as they may be more sensitive to the effects of BIIB105. The sample size of 3 was selected solely as precaution step before exposing participants with polyQ-ALS to 120 mg dose of BIIB105 in Cohort D2.

The sample size of Cohort D1 provides approximately █% power to detect a █% difference in the ratio to baseline in plasma NfL, in the BIIB105 versus placebo group, based on Cohort D1 120 mg data (N on BIIB105 = 36) vs pooled placebo data across Cohorts A through D1 (N = 19), with 2-sided █% significance level, assuming █% SD in both groups.

Assuming approximately █% drop out rate, the combined sample size of Cohorts D1 and D2 provides approximately █% power to detect a █% difference in the ratio to baseline in plasma NfL in the BIIB105 versus placebo group, based on pooled Cohorts D1 and D2 120 mg data (N=39) vs pooled placebo data across all cohorts (N=23), with a 1-sided █% significance level, assuming █% SD in both groups.

Part 2:

The sample size of Part 2 is based on the sample size of Part 1. Up to approximately 98 participants will be dosed in Part 2.

3. Definitions

3.1. Dates and Points of Reference

Unless stated otherwise, baseline data for Part 1 and Part 2 are defined as the last data collected prior to the time and/or on the date of first dose in Part 1 or Part 2, which is usually the same day as the Day 1 Predose/Baseline Visit. If baseline data at Day 1 predose/Baseline visit are missing, the last non-missing data prior to dosing (including data from Screening) will be used as baseline. For PD biomarkers, if predose baseline data (Day 1 predose/baseline or screening data prior to dosing) are missing, the non-missing data collected within 24 hours after first dosing will be used as baseline.

CONFIDENTIAL

The information contained herein may not be used, disclosed, or published without the written consent of Biogen MA Inc.

For the safety and PK data in the integrated analysis of Part 1 and Part 2, the baseline is defined as the day when the subjects receive their first dose of BIIB105 (60 mg or 120 mg) either in Part 1 or Part 2.

For PD, and efficacy data in the integrated analysis of Part 1 and Part 2, only participants from Part 1 Cohorts D1 and D2 are included. The baseline is defined as the Day 1 of Part 1 for the included subjects from Part 1.

Windowing and mapping will be applied to visits from both Part 1 and Part 2 to obtain analysis visits for the integrated analysis. Study day of a visit is calculated as (visit date – Day 1 or baseline) for a date before baseline, and as (visit date – Day 1 or baseline +1) for a date on or after baseline, respectively.

Only data from post-baseline unscheduled visits and early termination visits will be assigned to appropriate scheduled post-baseline visits using a windowing scheme as specified below by the target, lower, and upper study days. There will be no visit windows applied to scheduled visits. Once these visits have been windowed, a mapping algorithm will be applied to all available visits included for presenting by-visit summaries and analyses since Part 1 baseline.

For ALSFRS-R visits from Part 1 for subjects from Cohorts D1 and D2, for example, we follow the table:

Table 1 Analysis Visit Windows for ALSFRS-R – Part 1 Cohorts D1+D2

Analysis Visit	Visit in Part 1	Target Day	Lower Bound (inclusive)	Upper Bound (inclusive)
Baseline	Day 1	1	Last record prior to dosing	Last record prior to dosing
Week 4	Day 29	29	16	32
Week 5	Day 36	36	33	46
Week 8	Day 57	57	47	60
Week 9	Day 64	64	61	74
Week 12	Day 85	85	75	88
Week 13	Day 92	92	89	102
Week 16	Day 113	113	103	116

CONFIDENTIAL

The information contained herein may not be used, disclosed, or published without the written consent of Biogen MA Inc.

Week 17	Day 120	120	117	130
Week 20	Day 141	141	131	144
Week 21	Day 148	148	145	158
Week 24	Day 169	169	159	172
Week 25 ^a	Day 176	176	173	190
Week 25 ^b	Day 176	176	173	195
Week xx ^b	Day 214	214	196	236
Week xx ^b	Day 259	259	237	273

^a: For Cohorts D1, D2 participants who enter Part 2 after Part 1 treatment period.

^b: For Cohorts D1, D2 participants who do not enter Part 2 after Part 1 treatment period.

Windowing of the safety follow up visits in Part 1 (i.e. Day 214 and Day 259 for those participants from Cohorts D1 and D2 who do not enter Part 2 after Part 1 treatment period), Day 1 and unscheduled/ET visits in Part 2 for endpoints assessed every 4 weeks in Part 2 will follow the table below:

Analysis Visit	Target Day	Study days for unscheduled/ET visit	
		Lower Bound (inclusive)	Upper Bound (inclusive)
Week 24	169	156	183
Week 28	197	184	211
Week 32	225	212	239
Week 36	253	240	267
Week 40	281	268	295
Week 44	309	296	323

CONFIDENTIAL

The information contained herein may not be used, disclosed, or published without the written consent of Biogen MA Inc.

Week 48	337	324	351
Week 52	365	352	379
Week ww	ww *7 +1	ww*7-12	ww*7+15

[figure not shown]
For endpoints with assessment every 12 weeks in Part 2, i.e. HHD [REDACTED], their safety follow up visits in Part 1 (i.e. Day 214 and Day 259 for those participants from Cohorts D1 and D2 who do not enter Part 2 after Part 1 treatment period), Part 2 Day 1, unscheduled/ET visits will be mapped as follows.

Analysis Visit	Target Day	Study days for unscheduled/ET visit	
		Lower Bound (inclusive)	Upper Bound (inclusive)
Week 24	169	156	183
Week 28	197	184	225
Week 40	281	253	309
Week 52	365	337	393
Week 64	449	421	477
Week 76	533	505	561
...
Week ww	ww *7 +1	ww*7-28	ww*7+28

[REDACTED]
[REDACTED]
[REDACTED]
[REDACTED]

CONFIDENTIAL

The information contained herein may not be used, disclosed, or published without the written consent of
Biogen MA Inc.

Mapping of visits in Part 2 will depend on the Day 1 of Part 2.

- First, study day since Part 1 baseline for Part 2 Day 2 will be compared with the above table for windowing unscheduled/ET visits.
- If the Day 1 of Part 2 falls in the study day interval for Week 28, then the subject's visits in Part 2 will be mapped continuing the sequence of visits in Part 1 starting from Week 28, Week 32 etc.
- If the Day 1 of Part 2 falls into a window corresponding to a later analysis visit than Week 28, then all the remaining visits in Part 2 will be shifted accordingly. For example, if the Day 1 of Part 2 falls into the interval for Week 32, then the remaining visits in Part 2 will be labeled Week 36, Week 40 etc as follows.

Analysis Visit	Part 2 visit if Day 1=> Week 28	Part 2 visit if Day 1 => Week 32	Part 2 visit if Day 1 => Week 36
Week 28	Day 1	<skipped>	<skipped>
Week 30	Day 15	<skipped>	<skipped>
Week 32	Day 29	Day 1	<skipped>
Week 36	Day 57	Day 29	Day 1
Week 40	Day 85	Day 57	Day 29
Week 44	Day 113	Day 85	Day 57

CONFIDENTIAL

The information contained herein may not be used, disclosed, or published without the written consent of
Biogen MA Inc.

Week 48	Day 141	Day 113	Day 85
Week 52	Day 169	Day 141	Day 113
...

For endpoints with assessment every 12 weeks in Part 2, i.e. HHD, [REDACTED] their visits will be mapped as follows.

Analysis Visit	Part 2 visit if Day 1=> Week 28	Part 2 visit if Day 1 => Week 32
Week 28	Day 1	<skipped>
Week 30		<skipped>
Week 32		Day 1
Week 40	Day 85	Day 85
Week 52	Day 169	Day 169
Week 64	Day 253	Day 253
...

CONFIDENTIAL

The information contained herein may not be used, disclosed, or published without the written consent of
Biogen MA Inc.

Mapping visits may be handled case by case as well, if appropriate.

Visit mapping for other endpoints will follow the same logic as ALSFRS-R.

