Part 2 is an open-label extension study to assess the long-term safety, tolerability, pharmacokinetics, pharmacodynamics, and effects on disease progression of BIIB105 administered IT to adults with ALS and polyQ-ALS who complete Part 1 through Week 25.

The purpose of this final Statistical Analysis Plan (SAP) is to describe in detail the planned statistical analyses on final data from Part 2 and selected integrated data from 275AS101 Part 1 and Part 2 as of the final database lock to support the final clinical study report (CSR).

The study was terminated early by the sponsor based on the results from study 275AS101 Part 1 and integrated interim results from Part 1 and Part 2 which indicated there was no effect in neurofilament and no clinical benefit in patients treated with BIIB105. The statistical analyses are being simplified for an abbreviated CSR due to the early termination of the study.

2. Study Overview

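### The final SAP's 12-weekly (HHD) windows leave 27 of every 84 days from Day 226 uncovered, the general formula is one day below the listed rows, and there is no Week 32 row

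*SAP*

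**What the plan says.** Section 3.1 of the final SAP opens the table with "For endpoints with assessment every 12 weeks in Part 2, i.e. HHD" and states which visits it covers: "Part 2 Day 1, unscheduled/ET visits will be mapped as follows", plus the Part 1 follow-up visits of Cohort D1 and D2 participants who do not enter Part 2. The columns are analysis visit, target day, lower bound and upper bound:

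- "Week 28 197 184 225"
- "Week 40 281 253 309"
- "Week 52 365 337 393"
- "Week 64 449 421 477"
- "Week 76 533 505 561"

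The last row is general: target `ww*7+1`, lower bound `ww*7-28`, upper bound `ww*7+28`.

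Other text that bears on this:

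- The same section assigns unscheduled and early-termination (ET) data to visits by these windows. Scheduled visits are not windowed.
- The 4-weekly table just above has contiguous rows (for example Week 28 = 184-211, Week 32 = 212-239) and the general row `ww*7-12` to `ww*7+15`.
- The HHD mapping table further on has a column for participants whose Part 2 Day 1 is labelled Week 32.
- Section 3.1 also allows visits to be mapped case by case, and section 5.1 has all data listed unless otherwise specified.
- In the Part 2 schedule of activities, HHD is marked at Dose 1, at the 12-weekly maintenance visits and at Final/ET, but not at unscheduled visits. Final/ET is timed 90 days after the last dose, plus or minus 3.
- Section 5.6.3 specifies one HHD contrast, the Week 40 change from baseline, by ANCOVA on multiply imputed data.

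**The concern.** A windowing table should give every off-schedule assessment a single home, or say what happens to those without one. This table does neither. Its formula also fails to regenerate its own rows, so two programmers could implement it differently.

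The exposure is real. Section 1 of the final SAP says "The study was terminated early by the sponsor", so Final/ET visits with HHD follow last doses at various points in the schedule. A value without an analysis visit has no place in a by-visit summary. Nor can it serve as one of the postbaseline values in the imputation model of section 5.6.1. Its placement is left to discretion in a plan dated 05 September 2024, after an unblinded interim analysis with database lock on 29 April 2024 (section 4.1).

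**Working it through.** **Inputs.** Listed rows and general rows: final SAP 3.1. HHD visits and Final/ET timing: Part 2 schedule of activities.

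**1. Does the general row reproduce the listed rows?**

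| Visit | Target | Listed | `ww*7-28` to `ww*7+28` | Target ± 28 |
|---|---|---|---|---|
| Week 40 | 281 | 253-309 | 252-308 | 253-309 |
| Week 52 | 365 | 337-393 | 336-392 | 337-393 |
| Week 64 | 449 | 421-477 | 420-476 | 421-477 |
| Week 76 | 533 | 505-561 | 504-560 | 505-561 |

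It does not. It is one day early at both ends because it is centred on `ww*7`, while the target is `ww*7+1`. The formula that matches is `ww*7-27` to `ww*7+29`. In the 4-weekly table all eight listed rows match their own formula.

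**2. Which days are uncovered?** Gap = next lower bound − previous upper bound − 1.

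- Week 28 to 40: 253 − 225 − 1 = 27 (days 226-252)
- Week 40 to 52: 337 − 309 − 1 = 27 (days 310-336)
- Week 52 to 64: 421 − 393 − 1 = 27 (days 394-420)
- Week 64 to 76: 505 − 477 − 1 = 27 (days 478-504)

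Each cycle is 57 covered + 27 uncovered = 84 days, and 27/84 = 32.1%. The general formula also leaves 27-day gaps. There is no gap between Week 24 (upper bound 183) and Week 28 (lower bound 184). The 4-weekly table has no gap days.

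**3. Week 32.** The 4-weekly table calls days 212-239 Week 32. In the 12-weekly table, days 212-225 are Week 28 and days 226-239 are nothing. The Week 32 column of the HHD mapping table therefore cannot be reached from the HHD window table.

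**4. Can a Final/ET visit land in a gap?** Assume, for illustration, that Part 2 Day 1 is study day 197. A last dose on Part 2 Day d is then study day 196 + d, and the Final/ET visit is day 286 + d.

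| Last dose (Part 2 Day) | Final/ET day | Listed window |
|---|---|---|
| 1 | 287 | Week 40 |
| 15 | 301 | Week 40 |
| 29 | 315 | none |
| 57 | 343 | Week 52 |
| 85 | 371 | Week 52 |
| 113 | 399 | none |
| 141 | 427 | Week 64 |
| 169 | 455 | Week 64 |
| 197 | 483 | none |

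Days 315, 399 and 483 stay uncovered across the 3-day tolerance (312-318, 396-402, 480-486). Under this assumption, from Day 29 on, one last-dose visit in three leads to a gap. The Part 1 follow-up Days 214 and 259, with their 3-day tolerance, fall inside Week 28 and Week 40.

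**5. What reaches the Week 40 ANCOVA?** When Part 2 Day 1 is Week 28, the Part 2 Day 85 visit is the scheduled Week 40 HHD. A participant who attends it has a Week 40 value, whatever happens to a later ET value. Of the last doses before Day 85 in step 4, only Day 29 gives an uncovered visit, on day 315.

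With midpoint bounds, Week 40 would be 281 − 42 + 1 = 240 to 281 + 42 = 323, so day 315 would count as Week 40. Of the 54 gap days either side of Week 40, 13 (240-252) and 14 (310-323) would join it, 27 in all. The rest would go to Week 28 or Week 52. Day 343 is Week 52 under either scheme.

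**The case against.** A reader might infer that about a third of ET and unscheduled HHD values are dropped and replaced by imputed values in the Week 40 analysis. The documents do not support that, for these reasons:

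- No visible text says such values are discarded. Case-by-case mapping is permitted and all data are listed. Redacted lines follow the table, so a handling rule there cannot be excluded. The Part 1 SAP (section 3.1) does keep unmapped unscheduled assessments out of summary statistics while listing them. That indicates the sponsor's convention but does not govern the final SAP.
- HHD is not marked at unscheduled visits, so exposure is essentially confined to Final/ET visits. Those are tied to the last dose, so 32% is a share of calendar days and not an expected loss.
- The formula slip moves only edge days. It causes no loss by itself.
- Most gap-day values would not bear directly on Week 40 (step 5).

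A 28-day cap may also be deliberate. In a fast-progressing disease, leaving a distant value unassigned and imputing is defensible. But no cap is stated, the 4-weekly and ALSFRS-R tables in the same section are contiguous, and the Part 1 SAP spells out midpoint bounds.

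For a Part 2 Day 1 on days 226-239, the 4-weekly table does supply the Week 32 label. The mapping rule, however, points back to a table without naming it, and section 3.1 places Part 2 Day 1 for HHD under the 12-weekly table.

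These points remove the claim of loss. They leave the defects in the table itself.

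**Conclusion.** The table is internally inconsistent and incomplete. Both arithmetic findings are exact and need no assumption, and so is the missing Week 32 row.

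The consequence is narrower: Final/ET HHD values on uncovered days have no assigned visit and no visible pre-specified handling beyond discretion. That they would stay out of the by-visit summaries and the imputation model is an inference about the default. The one-in-three illustration assumes Part 2Day 1 on study day 197 and a Final/ET visit 90 days after the last dose. The direct effect on the Week 40 contrast is limited to participants without a scheduled Part 2 Day 85 HHD whose ET visit falls in a nearby gap. The documents do not say how many there are. This is a minor, inexpensive correction.

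**What to change.** Replace the 12-weekly bounds with contiguous midpoint bounds, following the sponsor's other tables:

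- Week 28 = 184-239 (upper bound 197 + 84/2 = 239)
- from Week 40, `ww*7-40` to `ww*7+43`, which gives Week 40 = 240-323, Week 52 = 324-407 and Week 64 = 408-491.

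Generate the listed rows from that formula so that the two agree. State which table labels Part 2 Day 1 for HHD, and reconcile that with the Week 32 column of the mapping table. This is still needed after the change, because the new Week 28 row overlaps the 4-weekly Week 32 window (212-239).

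If a 28-day cap is intended, say so, correct the general row to `ww*7-27` to `ww*7+29`, and state how values outside every window are handled.

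The cost is an edit to one SAP table and its mapping text. The downside of midpoint bounds is that an ET value may lie up to 42 days from its target (323 − 281 = 42).

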For integrated analyses of Part 1 and Part 2 for Cohorts D1 and D2, difference between treatment groups (i.e. Early-start BIIB105 120 mg and Placebo/Delayed-start BIIB105 120 mg) in least square means of Week 40 change from baseline with corresponding standard errors and 95% confidence intervals taken from the ANCOVA described in Section [5.6.1](#) based on the multiple imputation dataset.

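### Part 2/Integrated SAP 3.1: the 12-weekly (HHD) visit map contradicts the stated shift rule, so the HHD Week 40 contrast mixes measurements nominally 28 days apart

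*SAP*

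**What the plan says.** All references are to the Part 2/Integrated SAP unless stated.

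- **Shift rule (3.1).** If Part 2 Day 1 falls in a window later than Week 28, "then all the remaining visits in Part 2 will be shifted accordingly". The worked example reads "if the Day 1 of Part 2 falls into the interval for Week 32, then the remaining visits in Part 2 will be labeled Week" followed by the labels 36 and 40, in four-week steps.
- **4-weekly map (3.1).** The columns are entry at Week 28, Week 32 and Week 36. The relevant rows are "Week 40 Day 85 Day 57 Day 29" and "Week 44 Day 113 Day 85 Day 57". A Week 32 entrant therefore has Day 57 as Week 40 and Day 85 as Week 44.
- **12-weekly map for HHD (3.1).** The columns are entry at Week 28 and Week 32 only. Day 1 moves to Week 32 in the second column, but the later rows are "Week 40 Day 85 Day 85" and "Week 52 Day 169 Day 169", and Day 253 is Week 64 in both columns.
- **Role of windows (3.1).** Scheduled visits are not windowed, so their label comes from the map.
- **Entry check (3.1).** The first mapping step says that "study day since Part 1 baseline for Part 2 Day 2 will be compared with the above table". The bullets that follow it use Day 1.
- **HHD analysis (5.6.3).** The early-start versus delayed-start comparison is the difference "in least square means of Week 40 change from baseline with corresponding standard errors" and confidence limits, from ANCOVA on multiply imputed data.

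**The concern.** The shift rule covers all remaining visits, and one of the two maps printed beneath it does not shift. A single clinic visit then carries two analysis weeks depending on the endpoint. Because windows do not touch scheduled visits, nothing later in the plan corrects the label.

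The stake is the HHD Week 40 contrast. Late entrants would contribute strength measured at about Week 44 as if it were Week 40, in a disease where strength falls with time. ALSFRS-R at Week 40 would not have this mixture. Weeks 52 and 64 for HHD are affected in the same way.

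**Working it through.** **Inputs (3.1 and the Part 2 schedule of activities).**
- 4-weekly windows: Week 28 is days 184–211 (target 197), Week 32 is 212–239 (target 225), Week 36 is 240–267 (target 253), Week 44 is 296–323 (target 309).
- HHD windows: Week 28 is 184–225, Week 40 is 253–309, Week 52 is 337–393. There is no Week 32 row.
- HHD in Part 2 is done on Day 1, then Days 85, 169, 253 and so on. There is none on Day 57.

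**Formula.** Study day of a Part 2 visit = study day of Part 2 Day 1 + (Part 2 day − 1). Visits are taken on their nominal Part 2 day; the ±3-day visit allowance widens the ranges slightly.

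**The plan's own 4-weekly label.** The generic window runs from 7w − 12 to 7w + 15. For w = 44 this is 308 − 12 = 296 to 308 + 15 = 323. Week 32 entry puts Day 85 at 212 + 84 = 296 to 239 + 84 = 323, nominally 225 + 84 = 309. The 4-weekly label, Week 44, reproduces exactly.

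**Both maps for Part 2 Day 85.**

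| Entry | Day 1, study days (nominal) | Day 85, study days (nominal) | 4-weekly label | HHD label |
|---|---|---|---|---|
| Week 28 | 184–211 (197) | 268–295 (281) | Week 40 | Week 40 |
| Week 32 | 212–239 (225) | 296–323 (309) | Week 44 | Week 40 |
| Week 36 | 240–267 (253) | 324–351 (337) | Week 48 | no column |

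**Later HHD visits for Week 32 entrants.** Day 169 is 225 + 168 = 393, and (393 − 1)/7 = 56. Day 253 is 225 + 252 = 477, and (477 − 1)/7 = 68. The map prints Weeks 52 and 64.

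**What the Week 40 contrast contains.**
- HHD: days 268–295 (Week 28 entrants) and 296–323 (Week 32 entrants). Targets are 309 − 281 = 28 days apart, and the first and last days are 323 − 268 = 55 days apart.
- ALSFRS-R: Week 32 entrants use Day 57, at 212 + 56 = 268 to 239 + 56 = 295, the same range as Week 28 entrants.

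**Does the HHD label fit the HHD windows?** Day 85 lies in 253–309 only if Day 1 is on or before 309 − 84 = 225. That covers days 212–225, 14 of the 28 entry days. Entry on days 226–239 puts Day 85 at 310–323, which falls in no listed HHD window.

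**Size.** Elapsed time from baseline is 308 days against 280, and 308/280 = 1.10. Assume linear decline and let d be the difference between arms in the late-entry share. The spurious arm difference is then 0.10 × d of the 40-week decline:
- d = 0: none
- d = 10%: 1%
- d = 25%: 2.5%
- d = 50%: 5%

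With equal shares of 25% in both arms, the contrast is effectively at 0.75 × 40 + 0.25 × 44 = 41 weeks. These shares are assumptions; the documents give none.

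**Day 2 against Day 1.** If Day 1 is study day 211, Day 2 is 212. The first step then gives Week 32 and the next bullet gives Week 28. Only this boundary day is affected.

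**The case against.** The strongest reply is that the HHD table is deliberate. The shift example is a 4-weekly one. HHD has its own table, and with no Day 57 assessment it cannot follow the 4-weekly map to Week 40. Day 85 may have been chosen as the nearest visit: nominal day 309 is the upper bound of the HHD Week 40 window, and entry on days 212–225 counts as Week 28 by the HHD windows. It also keeps a real measurement in the analysis.

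That reading is possible, but the SAP states no such rule. It fits only half of the Week 32 interval. It also leaves the map's Week 32 column without a source, since the HHD windows have no Week 32 row and assign nothing to days 226–252.

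The reply is right about size. Protocol 5.3.2 allows Cohorts D1 and D2 to enter from four weeks after the last dose, nominally 169 + 28 = day 197, and the Week 28 interval closes 14 days later. Many may enter on time, although the SAP foresees later entry by printing Week 32 and Week 36 columns.

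The SAP also permits case-by-case mapping. It is dated 5 September 2024, after the unblinded interim analysis (lock 29 April 2024), so a written rule is preferable.

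A reader might infer more than the documents support:
- **That one arm is disadvantaged.** Arms are randomized and treatment stays blinded through Part 2 loading for D1 and D2. Nothing shows unequal late entry.
- **That Week 40 is the only HHD test.** It is the only time point named, but 5.6.1 provides models at other visits and Table 3 refers to several time points.
- **That a window rule is broken.** Windows do not apply to scheduled visits. The conflict is between the shift rule and the map.
- **That the Day 2 wording matters in itself.** It is an evident slip.

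**Conclusion.** The inconsistency stands. For Week 32 entrants the HHD map does not follow the SAP's own shift rule, and the HHD Week 40 contrast mixes measurements nominally 28 days apart. The certain effect is a blurred time point and added timing noise. Bias between arms needs unequal late entry; under linear decline it would be one tenth of the difference in late-entry share, as a fraction of the 40-week decline.

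The Week 40 versus Week 44 clash is specific to Week 32 entrants. Week 36 entrants have no HHD map at all. HHD is one of several functional measures in an abbreviated report after early termination, so the likely effect is modest. It should still be corrected, because the named HHD contrast depends on it.

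**What to change.** **Preferred.** Label Part 2 Days 85, 169 and 253 as Weeks 44, 56 and 68 for Week 32 entrants, and treat their Week 40 HHD as missing. Then do one of the following:
- Impute Week 40 from baseline and the Part 1 HHD visits that all D1 and D2 participants share.
- Interpolate between the observed Week 32 and Week 44 values. At nominal days the weights are (309 − 281)/(309 − 225) = 28/84 = 1/3 on Week 32 and 2/3 on Week 44.

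Do not add Week 32 and Week 44 columns to the by-arm imputation model in 5.6.1. No participant would have scheduled HHD at both Weeks 40 and 44, or at both Weeks 32 and 40. The scheduled data could not identify those associations, and the D1 and D2 placebo arms plan only about 12 + 6 = 18 participants.

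**Alternative, if a nearest-visit rule was intended.** Define HHD Week 40 as Part 2 Day 85, give its actual day range, and add a sensitivity analysis that excludes late entrants or adjusts for actual study day.

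**In either case.** Make the HHD entry windows and map columns agree: add the missing Week 32 row and Week 36 column, and assign days 226–252. Change Part 2 Day 2 to Part 2 Day 1 in the entry check.

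**Cost.** A table correction and a small programming change. Under the preferred route a few HHD Week 40 values become imputed or derived.
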